
a) Doppler ultrasound exams: power Doppler and LEAD ultrasound exams, performed during standard-of-care clinic visit or at research-only visit; if exam can be performed only with one of the two ultrasound scanners, only in one axis, or if one time point is missed entirely, subsequent exams may still be performed in full within their allowed time window.
 
b) Standard-of-care imaging: The baseline standard-of-care scan is generally within 6 weeks prior to initiating therapy, but may be greater than 6 weeks prior to therapy, if this is the scan that the treating physician chooses to use as reference for response evaluation. Preferably, this is a CT Chest-Abdomen-Pelvis (CAP) scan (with or without contrast), but it may also be an MRI or PET/CT or a combination of MRI and CT. At the discretion of the treating oncologist, the standard-of-care scan at week 12 may be performed outside of the +/- 4-week window.
 
c) Adverse event (AE) evaluation: Only AEs that are attributed to the study procedures are recorded and reported. During study procedures, study coordinator reminds patient to contact the clinical care team, if they experience any symptoms during the exam or afterwards. If the participant expresses to the coordinator that they have experienced symptoms during or after the exam, the coordinator will alert the clinical care team on the same day to contact the patient for AE evaluation and management. During baseline through week 12, patient will continue with standard-of-care provider visits at or outside of Stanford (generally, every 2-6 weeks, at the discretion of the treating clinical care team) including adverse event management. At week 12, a retrospective chart review will document any undisclosed study-related late adverse events and assure there are no ongoing study-related adverse events. If there is no adequate information in the medical record at week 12, patient will be contacted if needed to complete this documentation. Therefore, at minimum, there is one documented AE evaluation at week 12.
 
d) to be recorded once between baseline and study completion
 
e) may be obtained until study completion, even after a participant's death; patients or their outside medical providers may be contacted as needed to obtain the clinico-demographic data, if not available in the Stanford medical record.
 
f) to be quantified and recorded for all ultrasound exams from this study
 
g) RECIST measurements to be recorded for all imaging studies used for response evaluation (CT, MRI or PET/CT as described in footnote (b)). Performed at minimum at baseline and 12 weeks. RECIST measurements will also be recorded for other subsequent standard-of-care studies that the treating MD obtains at any interval to evaluate treatment response (until 12 months after initiating treatment or until end of the treatment that is being studied, whichever occurs first)
 
h) For combination treatments, initiation of therapy is typically defined by the day of starting treatment with the second drug, however another day (such as the start of treatment with the first drug) may be defined as start of treatment at the discretion of the Protocol Director; date considered start of treatment will be documented in the research procedure note in the electronic medical record.
 
i) 10 days is the minimum time period between week-3 and week-6 power Doppler ultrasound exams; similarly, 10 days is the minimum time period between week-3 and week-6 LEAD ultrasound exams; it is not required that power Doppler and LEAD ultrasound exams are performed on the same date.
 
j) Before end of study (3 years from date of study opening)
						

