## 9.2 Secondary Outcome Measures

Secondary endpoints are:

- 1) **initial relative change in tumor burden** (continuous): defined as relative change (i.e., difference between time points divided by value at time point 1, expressed as percentage) in the sum of all tumor diameters between treatment 'baseline' and first on-treatment response evaluation 8-16 weeks after start of treatment, using RECIST v1.1 for tumor diameter measurements, expressed as mean +/- standard deviation and median with interquartile range
- 2) **initial lesion response** (continuous): defined as the relative change in tumor diameter of a single lesion between treatment 'baseline' and first on-treatment response evaluation 8-16 weeks after start of treatment, using RECIST v1.1 for tumor diameter measurements, expressed as mean +/- standard deviation and median with interquartile range.
- 3) **12-month progression-free survival (PFS)** (yes/no): defined as not having experienced any PD per RECIST v1.1 within the first 12 months after initiating treatment (day 1 will be treatment start date), as a number and proportion without dispersion.

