### **9.2.1 Measurement Methods**

Tumor diameter measurements: same as for primary endpoint

Progression-free survival: determined by medical record review and contacting participants or their outside medical providers as needed.

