### **9.2.2 Measurement Time Points**

Initial response evaluation is performed by radiographic imaging at the same timepoints as for the primary endpoint. For repeat response evaluations on treatment, standard-of-care restaging imaging studies will be used. These, as well as determination of 12-month PFS, require follow-up at 12 months after initiation of treatment.

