## 10.4 Secondary Analysis

### 10.4.1 Analysis Population

All patients who have completed at least one LEAD and Doppler ultrasound exam at any time point. For correlation analyses, patients are included for each analysis based on availability of data points for specific analyses. If fewer than 20 patients in arm 1 and 10 patients in arm 2 fulfill these criteria for any secondary analysis, additional patient may be enrolled at the discretion of the Protocol Directors to have a complete dataset from 20 and 10 patients for this analysis, respectively.

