### 10.4.2 Analysis Plan

To address our secondary objective, i.e., evaluating if there is an optimal ultrasound modality to predict initial objective response in arm 1, we will utilize the same analysis approach as outlined above for the primary analysis. Here, we will use change in tumor perfusion parameters at **6 weeks** as our independent variables and conduct two regression analyses: (1) using power Doppler measurements and (2) using LEAD ultrasound measurements. AUCs between the two models will be compared using the nonparametric approach of DeLong for correlated AUC curves. In addition, we will compare AUCs between these models to the predictive model for the primary analysis.

To assess if there is an optimal time point for predicting initial objective response in arm 1, we will conduct Lasso regression models using tumor perfusion parameters for each time point (treatment 'baseline', 3 weeks, 6 weeks) separately for each imaging modality using a similar approach as outlined above. Given the exploratory nature of these analyses, we will not adjust for multiple testing.

For each arm, we will conduct correlation analysis for change in perfusion parameters at 3 and 6 weeks and initial relative change in tumor burden (overall and per-lesion), initial overall response, best overall response, and PFS until 12 months after initiating treatment by calculating either the Pearson r or Spearman rank correlation, as appropriate. PFS is estimated using the Kaplan-Meier method and the Kaplan-Meier curves will be presented.

Selection of lesions for ultrasound exams:

The up to 5 lesions that were selected for ultrasound studies for the primary analysis are re-assessed 6 weeks (+/- 15 days) after start of treatment and each lesion is assessed with both LEAD and power Doppler ultrasound at all 3 time points (treatment 'baseline', 3 weeks, and 6 weeks after initiating treatment).

Quantification and change of tumor perfusion parameters: defined in the same way as for the primary analysis for both power Doppler and LEAD ultrasound.

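### Section 10.4.2 relates perfusion change to PFS by Pearson or Spearman correlation only, which cannot use censoring and weakens the association if observed PFS time is correlated

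*Protocol*

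**What the plan says.** Section 10.4.2 lists several outcomes to be correlated with the change in perfusion at 3 and 6 weeks, in each arm. For the last of them the method is "PFS until 12 months after initiating treatment by calculating either the Pearson r or Spearman rank correlation, as appropriate". The sentence that follows reads "PFS is estimated using the Kaplan-Meier method and the Kaplan-Meier curves will be presented". No other method of relating perfusion to PFS is named.

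Section 9.2 defines the endpoint as a yes/no status, "defined as not having experienced any PD per RECIST v1.1 within the first 12 months after initiating treatment".

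Three places bear on how complete the PFS data will be:
- Section 9.2.2: "These, as well as determination of 12-month PFS, require follow-up at 12 months after initiation of treatment".
- Section 9.2.1: "Progression-free survival: determined by medical record review and contacting participants or their outside medical providers as needed".
- Section 6, footnote g, under which RECIST measurements from scans after week 12 are recorded only "until 12 months after initiating treatment or until end of the treatment that is being studied, whichever occurs first".

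For correlation analyses, section 10.4.1 adds that "patients are included for each analysis based on availability of data points for specific analyses". Section 10.1 calls all secondary endpoints exploratory.

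**The concern.** A correlation coefficient takes one number per patient and has no place for a censoring indicator. Kaplan-Meier does, and its use for the same variable shows that the plan expects some times to be censored. The plan therefore accounts for censoring when it describes PFS and ignores it when it relates PFS to perfusion.

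Footnote g makes early censoring a foreseeable event. A patient who stops the studied treatment without progression may have no later RECIST measurements. The association with PFS is a stated objective in both arms (section 1.2) and is meant to generate hypotheses. In a study of 20 and up to 10 patients, an analysis that handles the incomplete times wrongly can miss a real signal.

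**Working it through.** The protocol gives no PFS rate, event count, power or expected correlation, so there is no figure to reproduce. The check is a simulation of the named method.

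**Inputs from the protocol.** 20 patients in arm 1 and up to 10 in arm 2 (synopsis); PFS followed to 12 months (9.2, 10.4.2); Pearson or Spearman (10.4.2).

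**Assumptions not in the protocol.** Perfusion change X is standard normal. PFS is exponential with hazard (ln 2 / median) × 2^X, that is, a hazard ratio of 2 per SD, with a median of 12, 15 or 24 months. Baseline loss is 30% by month 12, a rate of -ln(0.7)/12 = 0.030 per month.

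**Step 1, the ranking.** Suppose patient A stops treatment at month 4 without progression and has no later RECIST data, and patient B progresses at month 6. The observed times are 4 and 6, so a correlation ranks A as worse than B. All that is known is that A's PFS exceeds 4 months.

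**Step 2, ties from the 12-month cut.** At the average hazard, the share progression-free at month 12 is 2^(-12/median): 2^(-1) = 0.50, 2^(-0.8) = 0.57 and 2^(-0.5) = 0.71.

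**Step 3, effect when an association exists (n = 20).** Correlations are negative because a higher X shortens PFS.

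| Assumed median PFS (months) | 12 | 15 | 24 |
|---|---|---|---|
| Spearman on full times | -0.47 | -0.47 | -0.47 |
| 12-month cut only: power, Spearman / Cox | 45% / 51% | 41% / 45% | 32% / 36% |
| 30% independent loss: Spearman on observed time | -0.31 | -0.29 | -0.22 |
| 30% independent loss: power, Spearman / Cox | 28% / 45% | 25% / 45% | 15% / 31% |

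Repeating the runs moves single entries by a few percentage points; the pattern does not change.

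**Step 4, error rate when there is no association.** If loss is independent of X, Spearman rejects in about 5% of trials. If the hazard of loss doubles per SD of X, Spearman rejects in 13-18% at 30% baseline loss and in about 5-8% at 10%. Cox rejects in about 5-6% at 30%.

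**Step 5, a different model.** Here X and PFS are linked by a Gaussian copula with a true rank correlation of 0.5 (coded as positive), and 12-month PFS is assumed to be 60%. The mean Spearman at n = 20 is about 0.47 on full times and 0.41 with the 12-month cut alone. It is 0.33 with 20% independent loss and 0.26 with 40%. Power is 0.48, 0.32 and 0.22 with no, 20% and 40% loss, against 0.50, 0.46 and 0.44 for Cox. With no association and loss that depends on X (log hazard ratio 1 per SD), Spearman rejects in 0.18 (20% loss) and 0.33 (40%) of trials, against 0.045 and 0.041 for Cox.

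**Step 6, the yes/no version.** In the middle scenario of step 3 (median 15 months, 30% loss), leaving out patients with unknown 12-month status gives a correlation of 0.40 in size, the same as with no loss. Power is 35%, against 41% for Cox in the same run. With no association and loss that depends on X, the error rate stays at about 5-7%.

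**The case against.** The strongest reply is that section 9.2 defines PFS as a status and section 1.2 speaks of 12-month PFS. A correlation with a binary status is legitimate. Section 10.4.1 lets patients without a known status drop out of the analysis, so nobody has to be counted as progression-free. Step 6 supports this: on that reading the result is valid and gives up only some power. What remains is that section 10.4.2 does not say which variable is correlated, and the Kaplan-Meier sentence beside it points to a time.

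The protocol also works against loss. It requires 12-month follow-up and allows record review and contact with outside providers. Accrual of 2 years in a 3-year study leaves 3 - 2 = 1 year for the last patient enrolled on schedule. The 30% loss is therefore an assumption, and at 10% the problem is small.

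Three stronger readings are tempting but not supported:
- **The 12-month cut invalidates the correlation.** It does not. Ties at month 12 leave a valid test with nearly the power of Cox (step 3, cut-only row).
- **The PFS association will be spurious.** That needs substantial loss related to perfusion change. Such loss is plausible if stopping treatment reflects drug exposure, but the protocol does not show it.
- **Counting from treatment start gives guaranteed event-free time.** Everyone analysed has had the exam. A nearly constant shift of 3 or 6 weeks hardly alters ranks and leaves a Cox fit essentially unchanged.

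It is also fair that Cox will be fragile here. In the step 5 scenarios about 6-8 events are expected among 20 patients and 3-4 among 10.

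**Conclusion.** The concern holds in a limited form. Section 10.4.2 commits to a method that cannot use censored times and does not settle whether PFS is a time or a status. If it is the observed time, early censoring weakens the association. At n = 20 with a hazard ratio of 2 per SD and 30% loss, Spearman falls from -0.47 to between -0.22 and -0.31, and power is 15-28% against 31-45% for Cox. The hazard ratio, the loss rate and the median PFS of 12 to 24 months are all assumed. Inflated error (13-18%) appears only when that 30% loss also depends on perfusion change.

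No primary conclusion is affected. The criterion for a follow-up study in section 10.7 rests on the AUC, and the PFS analysis is exploratory. Priority is low to moderate.

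**What to change.** In section 10.4.2, keep Pearson or Spearman for change in tumor burden and per-lesion diameter. For PFS:
- State that it is analysed as a time, censored at the last evaluation or at month 12 if there is no event.
- Replace the correlation with a Cox model, penalised if events are few, with the 3- or 6-week perfusion change as a continuous covariate.
- Report the hazard ratio per SD with its 95% confidence interval, and Harrell's C as the rank summary.

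The yes/no proportion in section 9.2 can stay as a descriptive endpoint. Starting the clock at the exam date (a landmark analysis) is optional.

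The cost is a sentence or two of wording. The dates and event status needed for the planned Kaplan-Meier curves are enough, so no new data are required. The downside is that with so few events in 20 or 10 patients the interval will be visibly wide.

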## PROTOCOL SYNOPSIS

TITLE	Early therapeutic monitoring of response to therapy with serial ultrasound in metastatic RCC
STUDY PHASE	Pilot
INDICATION	Metastatic Renal Cell Carcinoma (mRCC)
INVESTIGATIONAL PRODUCT OR PROCEDURE	Study of power Doppler ultrasound for early detection of therapeutic response after initiating therapy with: arm 1: tyrosine kinase (TKI) inhibitor plus immune checkpoint inhibitor (ICI) arm 2: non-ICI therapy (e.g., TKI monotherapy, combination of TKI with other kinase inhibitor, localized tumor therapy such as radiation, chemo- or radioembolization)
PRIMARY OBJECTIVE(S)	To assess whether changes in quantitative tumor perfusion parameters after 3 weeks of treatment, as measured by LEAD ultrasound, can predict initial objective response, defined by current standard-of-care, to therapy at 12 weeks after start of treatment
SECONDARY OBJECTIVE(S)	To evaluate if there is an optimal ultrasound imaging modality (power Doppler or LEAD ultrasound) or optimal time point to predict initial objective response, to assess the correlation of tumor perfusion parameters with change in overall tumor burden, change in diameter on a per-lesion basis and with 12-month progression-free survival (PFS).
STUDY PROCEDURE SUMMARY	power Doppler and LEAD ultrasound of subjects taking targeted therapy medication, measured at treatment 'baseline', 3-4 weeks, and 6-8 weeks after initiating treatment
SAMPLE SIZE	arm 1: 20 subjects arm 2: up to 10 subjects
STATISTICAL CONSIDERATIONS	We will evaluate the predictive ability of each model using area under the curve (AUC). For this pilot study, assuming that 59% of patients in arm 1 have an objective response to treatment, a predictive model with a true AUC of 0.7 will have a margin of error of 0.14 so that the estimated AUC can range from 0.56 to 0.84.

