## 6. STUDY CALENDAR

	Pre-Study	Baseline (up to 28 days prior to initiating therapy) h	Standard-Of-Care Therapy			
			Week 3 (+/- 8 days) i	Week 6 (+/- 15 days) i	Week 12 (+/- 4 weeks) h	Before Study Completion j
Informed consent	X					
Doppler ultrasound exams a		X	X	X		
Standard-of-care imaging b	X				X	
Adverse event evaluation c				X		
Recording of age, race, ethnicity, sex, diagnosis, cancer stage, tumor histology, and drug treatment d,e				X (just once during any study timepoint)		
Documentation of lesions selected for ultrasound exam, scanners and modalities used, and imaged axis planes		X	X	X		
Quantification of tumor perfusion parameters f						X
Tumor diameter measurements g						X
Optional recording of medical history and other diagnoses, concurrent treatment and medication, additional treatment, follow-up, and survival data for future correlation studies e		X				X

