## **9. MEASUREMENTS**

### **9.1 Primary Outcome Measures**

The primary endpoint is initial objective response per RECIST v1.1 assessed 8-16 weeks after start of treatment, using standard-of-care imaging. expressed as a number and proportion without dispersion.

Initial objective response (yes/no): defined as having either Complete Response (CR) or Partial Response (PR) per RECIST v1.1 at first on-treatment response evaluation 8-16 weeks after initiating treatment.

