### 9.1.2 Measurement Time Points

At treatment 'baseline' (prior to starting treatment) and 12 weeks after start of treatment (+/- 4 weeks) standard-of-care radiographic imaging is performed for initial response evaluation.

No further follow-up is required for the primary endpoint.

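### The week-6 ultrasound window overlaps the response-scan window by two days, and no rule puts the exam before the scan it is used to predict

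*Protocol*

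**What the plan says.** Protocol section 10.4.2 has the selected lesions "re-assessed 6 weeks (+/- 15 days) after start of treatment", and the calendar in section 6 gives the same window. The synopsis places the later exams differently, at "3-4 weeks, and 6-8 weeks after initiating treatment".

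The endpoint, initial objective response, is determined in section 9.1 "at first on-treatment response evaluation 8-16 weeks after initiating treatment". Section 9.1.2 agrees: "12 weeks after start of treatment (+/- 4 weeks) standard-of-care radiographic imaging is performed for initial response evaluation". Footnote b of the calendar then allows, at the treating oncologist's discretion, that "the standard-of-care scan at week 12 may be performed outside of the +/- 4-week window". It gives no earliest date.

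The only spacing rule for the ultrasound exams is in footnote i: "10 days is the minimum time period between week-3 and week-6 power Doppler ultrasound exams", with the same interval for LEAD. It does not refer to the response scan. The analysis populations in sections 10.3.1 and 10.4.1 do not exclude an exam done on or after that scan.

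Section 10.4.2 enters 6-week values as predictors of initial objective response in two ways: as change from baseline (one model per modality, also compared with the primary model), and as single-time-point values (again per modality) in the search for an optimal time point.

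**The concern.** A predictor has to be measured before the outcome it predicts. If a week-6 exam may fall on or after the response scan, the AUC of a 6-week model partly describes concurrent or retrospective association. The rationale in section 2.4 is to detect response or resistance earlier than the scan at about 12 weeks does, and a value obtained alongside the scan cannot serve that purpose.

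The 6-week models are exploratory but not idle. Under section 10.7, any model with an AUC of at least 0.7 leads to a follow-up study, and the model with the best AUC is carried forward. A 6-week model could therefore set the direction of the next study.

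**Working it through.** This is calendar arithmetic, counting the start of treatment as day 0.

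**The plan's own figure.** Week 12 ± 4 weeks (sections 6 and 9.1.2): 12 − 4 = 8 and 12 + 4 = 16 weeks, or 84 − 28 = day 56 and 84 + 28 = day 112. This reproduces the 8 to 16 weeks of section 9.1.

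**Exam windows.**
- Week 6 ± 15 days (sections 6 and 10.4.2): 42 − 15 = day 27 to 42 + 15 = day 57.
- Week 3 ± 8 days (sections 6 and 10.3.2): 21 − 8 = day 13 to 21 + 8 = day 29.
- Synopsis, 6 to 8 weeks: day 42 to day 56. The upper end still touches day 56.

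**Overlap.** The week-6 window ends on day 57 and the response window opens on day 56, so they share 57 − 56 + 1 = 2 days. Section 9.2 counts the start date as day 1 for progression-free survival. On that count the windows are days 28–58 and 57–113, with the same two-day overlap.

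**Permitted day combinations.** There are 31 exam days × 57 scan days = 1,767 pairs. The exam is on or after the scan in three, written as (exam, scan): (56, 56), (57, 56) and (57, 57). Only (57, 56) is strictly after, by one day. This counts what the text allows and is not a probability.

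**Lead time to an in-window scan.** Shortest: 56 − 57 = −1 day. Longest: 112 − 27 = 85 days.

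**Primary predictor.** 56 − 29 = 27 days between the end of the week-3 window and the opening of the response window.

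**Early scan under footnote b.** If a scan on day 49 supplied the endpoint, every week-6 exam from day 49 to day 57 would be on or after it. For a scan on day 42, the exam could follow by up to 57 − 42 = 15 days. Both cases are conditional on such a scan counting as the endpoint.

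**Would a narrower window be enough?** A half-width of 13 days ends on day 55, before the response window opens. With 14 days the windows meet on day 56, and with 15 days they overlap. No half-width in this range covers a scan before week 8.

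**How much one exam could matter.** With 20 patients and 59% responders (section 10.5), 0.59 × 20 = 11.8, so about 12 responders and 8 non-responders, giving 12 × 8 = 96 pairs. Re-ranking one non-responder, with the other scores held fixed, moves an empirical AUC by at most 12/96 = 0.125. For one responder the limit is 8/96 = 0.083. These are ceilings, not estimates.

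**The case against.** The strongest reply is that the defect is nearly nil. It needs a week-6 exam at the very end of its window and a response scan at the very start of its own, in the same patient. The analyses concerned are declared exploratory, the primary analysis is clear of the problem, and section 10.7 requires validation in an independent cohort. All of this stands and sets the weight of the point.

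Three stronger readings are tempting, and the documents do not support them.

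- *The exam can follow the scan by up to two weeks.* A reader might infer this from footnote b. But that footnote only frees the scan date; it does not say that an out-of-window scan supplies the endpoint, and section 9.1 read literally says it does not. What remains is that the protocol never says how such a scan is handled, and section 10.3.1 asks only that response be evaluable per RECIST, without restating the window. Section 5.1 gives partial protection: a patient who starts a different treatment has no further ultrasound exams. It does not cover patients who continue.
- *The 6-week AUC is inflated.* It can be. But nothing in the documents shows that perfusion measured on day 57 rather than day 55 changes the ranking of patients.
- *The sonographer knows the response.* The protocol states no blinding, but section 4 says the exams receive no formal interpretation. Quantification is scheduled for any time before study completion, so knowledge of response at that step could affect every exam, including week 3. An ordering rule would not remove that.

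It can also be said that exclusion of mistimed exams belongs in a statistical analysis plan. That is fair for the modelling rule. The order of exam and scan, however, follows from windows that the protocol itself fixes.

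**Conclusion.** The point holds in a limited form. As written, the plan permits a 6-week predictor to be taken on the scan date or, in one day combination, a day after it. The overlap is two calendar days under either day count. It rests on the stated windows and on the absence of any rule ordering exam and scan.

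A larger exposure depends on a scan before week 8 being used as the endpoint. Footnote b and section 9.1 leave that open between them and must be reconciled.

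Only the exploratory 6-week models and their AUC comparisons are touched. The documents do not allow the number of affected patients, or the size of any bias, to be computed. This is a worthwhile small improvement, not a threat to the study's main conclusion.

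**What to change.** 1. In footnote i of the calendar and in section 10.4.2, state that the week-6 power Doppler and LEAD exams are to be done before the response scan. An exam on or after the scan date is described but not used in any model predicting that response. Unlike a narrower window, this rule also covers early scans.
2. Reconcile footnote b with section 9.1 by stating whether a scan outside 8 to 16 weeks supplies the endpoint.
3. Report the exam-to-scan interval for each exam time point. The ordering rule alone does not guarantee useful lead time: an exam on day 55 with a scan on day 56 would still qualify.

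The cost is a few sentences, and an occasional late week-6 exam is lost to the 6-week models. The primary analysis and the sample size do not change.
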